introduce the study and ask if they are interested in learning more. If the patient agrees and would like more information about the study, the nephrologist/nurse practitioner will ask them to sign a DaVita “HIPAA Authorization to Use and Disclose Information for Research Purposes” form so their information may be shared with our study team and we can provide them with more information about the study. DaVita will provide the Program Manager with a list of eligible potential participants with signed DaVita HIPAA authorization forms. Our research team will contact patients on the list either by phone or in-person to discuss the study and if they are interested and agree to participate, they will provide informed consent and enrolled.

Participants will be enrolled at 4 locations in New York City: The Lower Manhattan Dialysis Center 1, The Lower Manhattan Dialysis Center 2, River Renal Services, Inc. and Chinatown Dialysis Center, LLC. The NYU Langone Health study team will analyze and collect data for this study.

Timeline: We will administer the interventions in two waves. In wave 2 (2 years after the start of the study), we will return to the dialysis centers in the first wave and begin enrollment again. This will allow us to identify new HD patients at each center. We will allow 1 month for identification of participants, initial contact by a research assistant, and baseline assessment as described below. Participants will be followed for 1 year after the end of the intervention for mortality and hospitalization.

Randomization:

We will randomize participants after completion of the baseline assessments. Participants will be block randomized (i.e., stratified over time) and stratified by sex, race/ethnicity, and dialysis center. They will be randomly assigned to one of the four study arms using a blind and secure computer based allocation system: **a) 6 months of CT alone, b) 6 months of ET alone, c) 6 months of CT+ET, d) standard of care.** We will use block sizes of four to ensure desired sizes in each arm. Given the nature of our interventions, it is not possible to blind the participant, treating provider and other HD center staff.

Intradialytic Interventions to Preserve Executive Function:

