Data will be analyzed according to the intention-to-treat principle. We will test the main effect of CT alone (arm 1) and the main effect of ET alone (arm 2) as well as the interaction between CT+ET (arm 3) compared with SC (arm 4). Baseline characteristics will be compared among treatment groups to test adequacy of randomization and identify possible confounders. If there are concerns about imbalances between treatment groups with respect to important risk factors for executive function decline, we will adjust regression-based models as necessary to account for these differences. Competing events (death or KT) will be quantified; if relevant, sensitivity analysis accounting for competing events will be performed.

1.0. Analytic Methods. Effect of CT, ET, and CT+ET on cognitive outcomes:

Change in executive function between baseline and 3 months will be a continuous outcome. Using a linear regression with the cluster option to account for the centers, we will test the null hypothesis (H01) of no difference in the mean change in executive function in CT alone vs. SC against the alternative hypotheses (HA1) that CT alone has a different mean change in executive function than SC. We will then test the null hypothesis (H02) of no difference in the mean change in executive function in ET vs. SC against the alternative hypotheses (HA2) that ET has a different mean change in executive function than SC.

In addition to these two main effects, we will test the effect of CT depends on ET (interaction). The null hypothesis (H03) is that there is no difference in the mean change in executive function for those in the CT, ET, CT+ET or SC arms vs. the alternative hypothesis (HA3) that at least one of the mean changes in executive function differs.

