H05 Not rejected	Arms 1 and 3 are superior to arm 4, but there is not sufficient evidence to distinguish arm 1 from arm 3; i.e., CT+ET is an effective strategy compared with SC, but we cannot tell if the CT+ET is effective beyond that of CT alone.	There is insufficient evidence to distinguish arm 3 from arm 4 and arm 1 from arm 3; i.e., CT+ET is not an effective strategy compared with SC and no better than CT alone.
H06 Rejected	Arm 2 is superior to arm 4 and arm 3 is superior to arm 2; i.e., both CT+ET and ET alone are effective strategies compared with SC but CT+ET is more effective.	Arm 3 is superior to arm 2, but there is not sufficient evidence to distinguish arm 3 from arm 4; i.e., CT+ET is not effective compared with SC but better than ET alone.
H06	Arms 1 and 3 are superior to arm 4, but there is not sufficient evidence to distinguish arm 1 from arm 3;	There is insufficient evidence to distinguish arm 3 from arm 4 and arm 2 from arm 3; i.e., CT+ET is not an effective

Not rejected	i.e., CT+ET is an effective strategy compared with SC, but we cannot tell if CT+ET is effective beyond CT alone.	strategy compared with SC and no better than ET alone.
--------------	--	--

Power Calculations: We used a Monte-Carlo simulation (1,000 randomly generated datasets) to estimate the power of a 2-by-2 factorial design with linear regression and Huber-White robust standard errors. We powered the RCT to detect a statistically significant difference in the CT+ET group based on a 3-month change in executive function, given the group mean change and SD in the pilot data.

When each arm of the study has 47 participants, we will have 80% power to detect a statistically significant change of 20 seconds between baseline and 3 months comparing the CT+ET arm to the SC arm. We will also have 95% power to detect a statistically significant change of 15 seconds in the CT arm and >99% to detect a statistically significant change of 18 seconds in the ET arm. Therefore, we would need to recruit 200 participants from 16 centers (approximately 13 participants per center). Even if we were to recruit just 22 participants (rather than 47) into each arm of the study, we would still have >80% power to observe statistically significant changes of 15 seconds for the main effects of CT and ET.

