Based on the pilot study we assumed an 88% consent rate per arm; this will leave approximately 57-60 participants from which we will need to recruit 50 per arm. We also accounted for 6% attrition in 3 months.

1.1. Change in Secondary Measures of Cognitive Function Over 6 Months. We will use a linear mixed model approach to describe the 3- and 6-month change in secondary cognitive function measures. We will construct a base model by fitting a single slope after enrollment. We will include two random effects: intercept and time relative to enrollment. This will allow for a unique trajectory for each participant, which varies randomly around the trajectory described by the fixed effects. The estimate for the time since enrollment variable will quantify the magnitude of the change in executive and global cognitive function (pre- and post-intervention) associated with CT, ET, and CT+ET. We will explore non-linear functions of time through cubic splines. The model is:

$$(CF_{ij} - CF_{i0}) = [\beta_{00} + \beta_{1i} \text{time}_{ij} + \beta_{01} X_i + \beta_{11} X_i (\text{time}_{ij})] + [b_{0i} + b_{1i} (\text{time}_{ij})] + r_{ij} + \varepsilon_{ij}$$

where time is time since enrollment, and X is the vector of interventions. We recognize that mortality may occur during the study and those who are survivors may be a distinct population and there may be differential mortality by intervention. If we find evidence for this differential survival, we will account for the unobservable executive and global cognitive function after death by 1) creating a composite endpoint that ranks mortality as worse than any change in executive or global cognitive function (composite endpoint), and 2) generate a causal model for change regardless of mortality using a survival-averaged causal effect model. As a sensitivity analysis, we will test that our findings are robust to the analytic approach using global z-scores.

2.0. Analytic Methods: Effect of CT, ET, and CT+ET on ESRD-specific clinical outcomes.

Staff at NYU Langone Health will help with data analysis. Data will be shared through a HIPAA Compliant Johns Hopkins REDCap database. The NYU Langone Health team will be conducting data analysis for all components of this study and requires all variables to do so.

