2.1. Time to Event Outcomes: Mortality. To examine the univariate association between study arm and mortality, separate product-limit estimated cumulative incidence curves will be calculated. Next, we will use a Cox proportional hazards model to estimate the association of study arm with time to the development of mortality. Censoring will occur at loss to follow-up or KT. The hazard function for the Cox model is:

$$\lambda(t|X_i) = \lambda_0(t) \exp(X_i \beta)$$

where x_i is the value of the covariate X for the i th participant, and $\lambda_0(t)$ is the baseline hazard function. If the proportional hazards assumption is not met, we will include an interaction with time.

2.2. Dichotomous Outcomes: Poor Lower Extremity Function, poor HRQOL, return to work, and amputation. We will test whether the study arm is associated with poor lower extremity function, poor HRQOL, return to work, and amputation using logistic regression or a modified Poisson regression (145), if the outcome is $>10\%$.

2.3. Count Outcomes: Number of Falls and Hospitalizations. We will use Poisson regression to test whether the study arm is associated with the number of falls and hospitalizations within the 3 months of the intervention.

3.0. Analytic Methods: Effect of CT, ET, and CT+ET on patient-centered outcomes.

Change in Patient-centered Outcome: For each patient-centered outcome, we will calculate a score. We will treat each patient-centered outcome as continuous and will estimate the change in these outcomes between baseline and 3 months. We will analyze each patient-centered outcome separately. We will analyze the change in these outcomes using the analytic plan described in 1.0.

3.1. Change in Patient-centered Outcome over 6 Months. Patient-centered outcomes are longitudinal data (3 and 6 months) and analyzed using the analytic plan described in 2.0 for repeated measures of executive function.

4.0. Treatment Effect Heterogeneity. Frailty has been associated with worse trajectories of executive function in older adults (146) and HD patients (16). Therefore, we will explore treatment heterogeneity between those who are frail and nonfrail in all primary and secondary outcomes. We will include an interaction term between frailty status and intervention type (study arm) to assess difference in treatment effect by frailty status. Using a similar approach, we will test for treatment effect heterogeneity by age, sex, and race/ethnicity.

Risks:

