We will keep all data collected strictly confidential so there is minimal risk of loss of confidentiality. All participating faculty and staff have received appropriate training in the responsible conduct of research, protection of human subject participants, and HIPAA regulations. All data collection instruments and consent forms will be kept in a locked cabinet. All questionnaires, assessments and cognitive function data will be stored in RedCap, a secured database. To maximize confidentiality, only the study investigators, data manager and key study personnel will have access to the information.

Data Safety Monitoring Board (DSMB) and Adverse Event Reporting:

An independent DSMB will be established to oversee the safety and progress of this trial, comprised of five individuals (a patient advocate, an ethicist, a statistician, a nephrologist, and a research nurse) who will serve in this capacity throughout the entirety of the trial. We will ensure that all members of the DSMB disclose of any conflicts of interest. The DSMB will have pertinent experience and review accumulating data from this RCT on a regular basis with the goal of enhancing the safety of the trial participants. A DSMB is warranted in this RCT because the study is being performed in a potentially vulnerable population, namely those with ESRD on HD and this population is at elevated risk of serious outcomes. A medical monitor will be included on the DSMB to review all events and determine whether they classify as AE's/ or SAE's.

We will monitor the number of injurious falls resulting in a medical encounter during the 6 months of interventions. This data will be obtained during the survey portion of our assessments by asking the participant to self-report the number of falls in the last 6 months. Additionally, falls during the intervention or assessment will be directly observed and recorded by study staff. Any falls will be reported to the medical monitor for review and determination whether they classify as an AE or SAE attributable to the interventions.

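### Section 2.3 tests falls and hospitalisation counts by Poisson regression with no allowance for overdispersion, and the later update leaves unclear whether that model still governs

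*Combined protocol and SAP*

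**What the plan says.** Section 2.3 is one sentence: "We will use Poisson regression to test whether the study arm is associated with the number of falls and hospitalizations within the 3 months". It gives no variance estimator, dispersion check, alternative count model or follow-up-time offset. Study arm has four levels, and 2.3 does not say which contrasts are tested.

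Protection against a wrong variance model appears elsewhere, for other analyses:
- Section 2.2 offers modified Poisson regression for binary outcomes.
- Section 1.0 analyses executive function "Using a linear regression with the cluster option to account for the centers".
- The power simulation uses "linear regression and Huber-White robust standard errors".
- The opening of Statistical Methods adds: "Competing events (death or KT) will be quantified; if relevant, sensitivity analysis accounting for competing events will be performed".

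The later update was written to deal with the COVID-19 shutdowns. Its Statistical Analysis section applies ANOVA, Kruskal-Wallis or chi-squared tests to secondary outcomes. It treats changes from baseline to 3 months in ESKD-specific clinical outcomes as continuous, by linear regression. Section 2.3 sits under heading 2.0, which covers ESRD-specific clinical outcomes. The update mentions neither falls, hospitalisations nor Poisson regression.

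**The concern.** Plain Poisson regression takes the variance of the counts to equal their mean. If participants within an arm differ in their underlying risk of falling or being admitted, the variance exceeds the mean, the model-based standard errors are too small, and the test rejects too often. The plan gives some reason to expect uneven risk, since section 4.0 looks for different effects by frailty in all primary and secondary outcomes.

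At stake are the between-arm comparisons of two secondary outcomes across four arms. A difference in falls or admissions could be declared at a nominal 5% when the true error rate is higher. A reader also cannot tell whether the counts are to be analysed by Poisson regression, by linear regression of a change, or by an ANOVA-type test.

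**Working it through.** **No figure to reproduce.** The documents state no event rate, variance, sample size or power for the counts. What follows is conditional on assumed values.

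**Inputs from the documents.** Two-sided 5% level (update, Statistical Analysis). Planned 47 per arm (Power Calculations). 121 randomised to four arms (update, Randomization), so 121/4 = about 30 per arm. 25 interrupted 3-month follow-ups (update, Study Design), so (121 - 25)/4 = 24 per arm. The figure of 24 assumes that the 25 are among the 121 and spread evenly, and it fits only counts taken from the 3-month survey. Hospitalisation is followed for longer: "Participants will be followed for 1 year after the end of the intervention for mortality and hospitalization".

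**Inputs assumed.** Variance/mean ratio phi = 1, 1.5, 2 or 3; mean 0.3, 0.5 or 1.0 events per person.

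**Large-sample size of the plain test.** Size = 2 x (1 - Phi(1.96/sqrt(phi))):
- phi = 1: 1.96/1.000 = 1.960, size 5.0%
- phi = 1.5: 1.96/1.225 = 1.600, size 11.0%
- phi = 2: 1.96/1.414 = 1.386, size 16.6%
- phi = 3: 1.96/1.732 = 1.132, size 25.8%

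**Simulation at the trial's sizes.** Null comparisons of one arm with standard care, 24 to 47 per arm. Counts are Poisson at phi = 1 and otherwise negative binomial with variance phi x mean. HC3 variance = HC0/(1 - 1/n)^2, with t on 4n - 4 degrees of freedom. Comparisons with no events in an arm (under 4%) are left out.

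| phi | Plain Poisson | Poisson, HC3 and t |
|---|---|---|
| 1 | 3-5% | 3-5% |
| 1.5 | 8-11% | 4-5% |
| 2 | 12-16% | 5-6% |
| 3 | 19-25% | 6-7% |

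Quasi-Poisson scaling gives about 1.5-5%. It is most conservative at 24 per arm, mean 0.3 and phi = 3.

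**How extreme the assumptions are.** For a mixed Poisson count, phi = 1 + mean x CV^2, where CV is the coefficient of variation of individual rates.
- Mean 1.0, phi = 1.5: CV^2 = 0.5/1.0 = 0.5.
- Mean 0.3, phi = 3: CV^2 = 2/0.3 = 6.7. Under the negative binomial, 3^(-0.15) = 85% of participants then have no event.

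High ratios at low means therefore need very uneven individual rates.

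**Cost of robust errors when none are needed.** At phi = 1 and a true rate ratio of 0.50, power from plain to HC3 is:
- 26.2% to 23.7% (24 per arm, standard-care mean 0.5)
- 50.7% to 47.9% (24 per arm, mean 1.0)
- 33.0% to 30.6% (30 per arm, mean 0.5)
- 59.9% to 57.8% (30 per arm, mean 1.0)

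**Centre.** With 15 centres, arms spread over all of them, mean 0.5, phi 1 to 3 and an assumed between-centre rate CV of 0 or 0.5, participant-level HC3 gives 3.6-7.3%. Centre-clustered errors give 4.5-8.1%. Allocation is within centre, so clustering is not needed for a valid test.

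**Offset.** The protocol says: "We also accounted for 6% attrition in 3 months". If 6% of one arm leave halfway and no one leaves the comparator, that arm's count is low by 0.06/2 = 3%. At 21% (25/121) within one arm it is 0.21/2 = about 10%. If the whole trial's loss fell in one of four arms, the shares of that arm would be 4 x 6% = 24% and 25/30.25 = 83%, and the counts would be low by about 12% and 41%. With equal loss in every arm the ratio is nearly unaffected.

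**The case against.** The strongest objection is that the update has replaced 2.3. It says the methods were updated, it names the class of outcomes to which the counts belong, and it assigns that class to linear regression. If so, the error rates above do not apply. This stands as a condition and not as a refutation. The update speaks of changes between baseline and 3 months, which does not plainly describe a count of events within 3 months, and it never names counts. The need to reconcile the two texts remains either way.

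It is also fair to say that the size rests wholly on assumed dispersion, and that the arm-versus-standard-care contrast is one choice among several that 2.3 leaves open. Taking the model from the protocol and some sample sizes from the update mixes two stages of the plan, but 47 per arm gives similar plain-Poisson results. HC3 is not the only remedy; quasi-Poisson would also serve. The HC3 form simulated is for an arm-only model, and the version with an offset was not simulated.

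Some stronger readings are tempting:
- **That the counts are overdispersed, or that the true error rate is 19-25%.** No rate or variance is given, and at a ratio of 1 there is no inflation.
- **That fall safety depends on this model.** Falls during the intervention or assessment are observed directly, and any fall goes to the medical monitor.
- **That the 3-month falls result includes time before randomisation.** The DSMB section does describe "asking the participant to self-report the number of falls in the last 6 months". However, Table 2 and the DSMB data-collection paragraph also list injurious falls self-reported at 3 and 6 months and falls observed directly. None of these is linked to 2.3, so a recall bias cannot be computed from the documents.

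**Conclusion.** The point holds, as a minor one. Section 2.3 specifies plain Poisson regression, and no other part of the plan supplies a variance allowance for the counts. If 2.3 governs and the variance/mean ratio is 1.5, the type I error of a nominal 5% comparison roughly doubles, to 8-11%. At ratios of 2 and 3 it reaches 12-16% and 19-25%. Robust errors bring this to 4-7%. The figures rest on assumed means of 0.3-1.0, assumed dispersion and 24 to 47 per arm.

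The comparisons affected are of secondary outcomes with no stated power. The primary Trail Making Test analysis is not touched.

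**What to change.** First state which text governs the counts. Then put in section 2.3, for example: *Falls and hospitalisations within 3 months will be analysed by Poisson regression on study arm with HC3 robust standard errors and a t reference, with a log follow-up-time offset where observed time differs between participants. Counts are not analysed by the linear change-score or ANOVA-type tests.* Quasi-Poisson scaling is an acceptable alternative.

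In the same place, name the source of the falls count and the contrasts to be tested. Treat an absent 3-month survey as missing data, since an offset cannot repair it.

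The change takes two or three sentences and no new data; the mortality analysis in 2.1 already needs dates of loss to follow-up and transplant. If the variance equals the mean, it costs about 2-3 points of power for a rate ratio of 0.50 at 24-30 per arm, and intervals are 1-3% wider. At ratios of 1.5, 2 and 3, intervals widen by 17-23%, 28-39% and 42-65%, which is the uncertainty that plain Poisson would leave out. At a ratio of 3 the HC3 test stays slightly liberal, at about 7%.

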Other patient-centered outcomes	Validated self-report instrument	PROMIS-29 short-form profile: anxiety, depression, fatigue, pain, perceived function, sleep disturbance, and participation in social roles/activities, ability to return to work	Baseline and at 3- and 6-month Follow-up
Demographics*	Self-report and abstraction	Age, sex, race/ethnicity, and education	Baseline
Health behaviors	Self-report and abstraction	Smoking status, alcohol intake, illicit drug use	Baseline and at 3- and 6-month follow up
Medical factors	Chart abstraction	History of chronic and infectious diseases	Baseline and at 3- and 6-month follow up
Clinical measures	Chart abstraction	BMI, eGFR, blood pressure, cholesterol	Baseline and at 3- and 6-month Follow-up
Dialysis factors	Chart abstraction	Time on dialysis, access site, schedule, cause of ESRD	Baseline and at 3- and 6-month Follow-up
DSMB Review	Direct observation	Falls during intervention or assessment, hypotension, hypertension, elevated heart rate	At every dialysis session
	Self-report	Cramping and headache	At every dialysis session
	Self-report	Injurious falls	Baseline and at 3- and 6-month Follow-up

All measures of executive function, global cognitive function, frailty, and the SPPB (walk speed, chair stands and balance) will be assessed in-person prior to the start of the dialysis session.

Assessment of Executive Function:

- *Trail Making Test A and B (TMTA and TMTB)* scores are validated measures of executive function (i.e., cognitive shifting, cognitive flexibility), attention, concentration, and psychomotor speed (5). These tests measure the time required to connect a series of sequentially numbered (TMTA) and numbered/lettered (TMTB) circles. Needing more time to complete the tests indicates worse executive function; times are capped at 3 minutes for TMTA and 5 minutes for TMTB.
- The *Stroop Test* (reading, color-naming, and interference sub-tasks) (103) evaluates the inhibitory control of executive function and involves reading the name of a color printed in a different color ink: **BLUE**. The time ratio of color-word interference and color-only tasks will be calculated.

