Follow-up Assessments: We will perform follow-up assessments at 3 months of intervention and 6 months of intervention (measures listed in Table 2) in the dialysis center using a similar approach to the baseline assessment for comparability of the measures. Research assistants blinded to the assigned study arm will perform follow up assessments.

The Principal Investigator/ Program Manager will inform the appropriate dialysis center treating nephrologist/nurse practitioner of any abnormal findings for cognitive function, anxiety, and depression at the 3 month and 6 month assessments.

Data collection for variables needed for DSMB review. Falls during the intervention or assessment will be directly observed by study staff at each intervention session throughout the whole study. Hypotension (SBP<110 mmHg or DBP<50 mmHg) and hypertension (SBP>150 mmHg or DBP>90 mmHg) will be identified during the clinical measurements of blood pressure that occur approximately 10 times throughout the dialysis session. Similarly elevated heart rate (>80% of maximum heart rate calculated as 220-participant age will be identified during the clinical measurements of heart rate that occur approximately 10 times throughout the dialysis session. Cramping and headaches will be noted if a participant tells the study staff that they are experiencing these events. Injurious falls for DSMB review outside of the dialysis session will be self-reported by participants as part of the questionnaire at 3- and 6-months follow-up.

Plan for Fidelity Monitoring. In the pilot study, there was a small dropout rate (3/23), which is consistent with other intradialytic exercise interventions at 6 months (86) and there is high compliance (88%) with ET (63). We will allow for temporary noncompliance due to acute illness or travel. We will add additional sessions onto the end of the intervention period (no more than 2 weeks) in any of the study arms, as has previously been proposed in intradialytic intervention trials (86). The Program Manager/Study Coordinator

will visit the dialysis centers administering these arms of the study monthly throughout the course of the intervention to give a refresher on the safe and effective use of the foot peddlers. The PI or project manager will visit each clinic weekly during the administration of the intervention to directly observe compliance and facilitate communication among the HD clinic staff, patients, and study staff. Research assistants will record the:

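### Section 2.3 names Poisson regression for falls and hospitalisations without a robust variance, and leaves open which fall question, window and definition it analyses

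*Combined protocol and SAP*

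**What the plan says.** Protocol section 2.3 (Count Outcomes) uses Poisson regression to test whether "the study arm is associated with the number of falls and hospitalizations within the 3 months of the intervention". It gives no data source, recall window, fall definition, variance estimator or offset. Elsewhere the plan does name a variance method. Section 1.0 fits the primary outcome "Using a linear regression with the cluster option to account for the centers", and Power Calculations simulated linear regression with Huber-White errors.

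Fall collection is described only for safety purposes, in three places:

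- Table 2, DSMB Review rows: "Injurious falls", self-reported at baseline, 3 and 6 months, with no recall window.
- Data collection for variables needed for DSMB review: injurious falls outside dialysis are "self-reported by participants as part of the questionnaire at 3- and 6-months follow-up", again with no window. Falls during sessions or assessments are observed by staff.
- Data Safety Monitoring Board (DSMB) and Adverse Event Reporting: "We will monitor the number of injurious falls resulting in a medical encounter during the 6 months of interventions". The data come from "asking the participant to self-report the number of falls in the last 6 months".

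On timing, the Randomization section says "We will randomize participants after completion of the baseline assessments". The Timeline says "Participants will be followed for 1 year after the end of the intervention for mortality and hospitalization".

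Section 2.3 sits under heading 2.0, on ESRD-specific clinical outcomes. The updated SAP (Statistical Analysis) treats baseline-to-3-month changes in that group of outcomes as continuous. It also applies ANOVA, Kruskal-Wallis or chi-squared tests to primary and secondary outcomes. It mentions neither falls, hospitalisations nor Poisson regression.

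**The concern.** There are two separate issues.

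The first is the model. Counts of falls and admissions often vary between people by more than a Poisson law allows. If so, model-based Poisson standard errors are too small and the arm comparison rejects too often. The plan guards against a misspecified variance for its primary outcome but says nothing for the counts. The updated SAP does not say whether the counts still follow 2.3 or moved to the continuous-change model or the group tests.

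The second is the fall outcome itself. The analysis window is 3 months; the only stated recall window is 6 months. The definition also shifts: all falls in 2.3, injurious falls in Table 2 and the data-collection text, and injurious falls with a medical encounter in the DSMB section, where the question asked is simply the number of falls. If the 6-month question supplied the 3-month count, falls from before randomisation would enter every arm and pull the rate ratio toward 1. In a trial with an exercise arm, a harm or a benefit on falls could then be missed. The recall issue concerns falls only, not hospitalisations.

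**Working it through.** The documents state no rate, dispersion, effect size or power for falls, so there is no planned figure to reproduce. Everything numerical below rests on assumed values shown as ranges.

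**Inputs.** Randomised: 121 (SAP, Randomization), so 121/4 is about 30 per arm. Interrupted 3-month follow-ups: 25 (SAP, Study Design), so (121 - 25)/4 = 24 per arm if every one of them lacks a fall count. Test: two-sided 5% (SAP). Assumed: control mean 0.2 to 0.8 falls per 3 months; dispersion 0, 1 or 2.

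**1. Type I error.** With gamma-Poisson counts, variance/mean = 1 + dispersion × mean. Over mean 0.4 to 0.8 and dispersion 1 to 2 this runs from 1 + 1 × 0.4 = 1.4 to 1 + 2 × 0.8 = 2.6. In large samples the plain Wald test rejects with probability 2 × (1 - Φ(1.96/√ratio)); at ratio 2 this is 16.6%. Simulation (two arms, no true difference, 20,000 trials per cell) gives these rejection rates, plain / robust, in %:

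| n per arm | mean | dispersion 0 | dispersion 1 | dispersion 2 |
|---|---|---|---|---|
| 24 | 0.2 | 1.7 / 2.0 | 2.9 / 2.4 | 4.2 / 2.9 |
| 24 | 0.4 | 4.2 / 4.8 | 8.4 / 5.9 | 11.8 / 6.2 |
| 24 | 0.5 | 4.2 / 4.9 | 9.6 / 5.9 | 14.9 / 7.0 |
| 24 | 0.8 | 4.2 / 5.0 | 13.8 / 6.6 | 20.9 / 7.4 |
| 30 | 0.2 | 2.7 / 3.3 | 4.2 / 3.7 | 5.4 / 3.7 |
| 30 | 0.4 | 4.3 / 4.9 | 8.4 / 5.6 | 12.7 / 6.4 |
| 30 | 0.5 | 4.5 / 4.8 | 9.9 / 5.8 | 15.0 / 6.8 |
| 30 | 0.8 | 4.4 / 5.2 | 13.4 / 6.4 | 21.3 / 7.1 |

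Repeating the simulation with a different seed changed cells by about half a point at most and put the highest robust figure near 8%.

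**2. Share of recall before randomisation, if the 6-month item is used at month 3.** (6 - 3)/6 = 50%.

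**3. Dilution, same condition.** Let k be the pre-randomisation rate divided by the later control rate. Observed rate ratio = (k + RR)/(k + 1).

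- k = 1: RR 0.50 gives 1.5/2 = 0.75; RR 2.0 gives 3/2 = 1.50.
- k = 0.5: 1.0/1.5 = 0.67 and 2.5/1.5 = 1.67.
- k = 2: 2.5/3 = 0.83 and 4/3 = 1.33.

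The expected difference in counts is unchanged, because (k + RR) - (k + 1) = RR - 1. The shared earlier falls attenuate the ratio and add noise; they do not create a difference.

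**4. Power, same condition, k = 1, no overdispersion.** SE(log RR) = √(1/events0 + 1/events1). At 30 per arm and mean 0.5:

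- RR 0.5, true 3-month count: events 15 and 7.5, SE 0.447, z = 0.693/0.447 = 1.55, power 34%.
- RR 0.5, 6-month recall: events 30 and 22.5, SE 0.279, z = 0.288/0.279 = 1.03, power 18%.
- RR 2.0: 59% falls to 40.5% by the same steps.

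**5. Adjusting for a baseline fall count** (24 per arm, mean 0.5, RR 0.5, dispersion 1 to 2, robust errors). The median rate ratio stays at 0.74 to 0.75, so the dilution remains. Power is 12% to 14% unadjusted. It is 21% to 22% if each person reports the same earlier falls identically at both visits, and about 16% if the two reports share only the person's underlying fall rate. The gain is therefore about 2 to 9 points. Null rejection with adjustment is about 7% to 9%, so part of the gain is not at equal type I error.

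**The case against.** The strongest objection is that the recall problem depends on a link the documents never make. The 6-month question is written for safety monitoring over the 6-month intervention and fits that purpose at the 6-month visit. No text says it feeds 2.3 or is worded that way at month 3, and the questionnaire is not in the documents. A reader might infer that half of the analysed fall time preceded randomisation in this trial. The documents do not support that: a separate 3-month question is not ruled out. This objection stands, so the dilution figures are conditional.

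On the model, silence about variance is not a commitment to model-based errors, and no dispersion is given. At a mean of 0.2 the inflation is negligible. This also stands; the point is that 2.3 should say which errors are used, given that the plan does so elsewhere.

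The figure of 24 per arm is a low case. The fall item belongs to the survey, and the baseline survey is done by phone, so an interrupted in-centre follow-up need not mean a missing count. The results at 30 per arm are much the same for type I error.

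The SAP is presented as an update for COVID-19 shutdowns, so sections it does not mention may simply stand. That is plausible, but its sentence on ESKD-specific clinical outcomes, read by heading, pulls the counts into linear regression. It cannot cover everything under 2.0, because mortality is not a baseline-to-3-month change. The status of the counts stays unresolved.

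A reader might also infer that adjusting for the baseline fall item would repair the comparison. It would not: the dilution remains, the larger power gain needs identical re-reporting of the same falls, and Table 2 gives no window for the baseline item.

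**Conclusion.** The concern holds as a modest one about a secondary outcome. Certain from the text: 2.3 names Poisson regression without robust variance, names no fall source, window or definition, and is not clearly carried into or replaced by the updated SAP. Conditional on overdispersion and model-based errors: type I error of about 8% to 21% at assumed dispersion 1 to 2 and mean 0.4 to 0.8, against about 6% to 8% with robust errors, and no clear inflation at mean 0.2 or with no overdispersion. Conditional on the 6-month item being used as worded at month 3: about half of the recall precedes randomisation, and at a constant rate 0.50 appears as 0.75 and 2.0 as 1.50.

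Two stronger readings are not supported. One is that a reported falls result is wrong; the documents contain no such result. The other is that safety oversight fails; falls during sessions are directly observed and sent to the medical monitor, so oversight does not rest on this question.

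**What to change.** 1. **Model.** Analyse falls and hospitalisations with robust-variance Poisson or negative binomial regression, with a log person-time offset where observation time differs. That mainly concerns hospitalisations; no size is claimed for the offset. State in the SAP that these counts follow 2.3 and not the continuous-change model. Cost: essentially none if counts are Poisson. If overdispersed, intervals widen by √(1 + dispersion × mean), from √1.4 = 1.18 to √2.6 = 1.61, that is 18% to 61% over the range used above.
2. **Outcome.** State which item and which fall definition feed 2.3. Do not report a 6-month recall as a 3-month count. If only the 6-month recall exists, label the 3-month comparison as diluted. Cost: SAP wording.
3. **Optional covariate.** The baseline fall item may be included for one parameter, with its limits stated: no removal of dilution, and a power gain of about 2 to 9 points at rate ratio 0.5 and dispersion 1 to 2.
4. **Design lesson only, because the trial has been terminated.** Ask at month 3 about falls since randomisation and at month 6 about falls since the last assessment. The pre-randomisation share then drops from 50% to 0%.
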